This material is the property of the NYU School of Medicine and Langone Medical Center. Do not disclose or use except as authorized in writing by the study sponsor

List of Abbreviations

ASA	American Society of Anesthesiologist Score
VAS	Visual analog scale
TSA	Total Shoulder Arthroplasty
ISB	Interscalene Nerve Block
DVT	Deep vein thrombosis
ER	Emergency room
AE	Adverse event
SAE	Serious adverse event
IV	Intravenous
PO	Taken orally
PRN	Taken as needed
TID	Taken three times per day
Q4h	Taken every four hours
CI	Confidence interval
SD	Standard deviation; a parameter, which characterizes a population distribution
SE	Standard error
ANOVA	Analysis of variance; a linear model
NSAID	Non-steroidal anti-inflammatory drug

CONFIDENTIAL

This material is the property of the NYU School of Medicine and Langone Medical Center. Do not disclose or use except as authorized in writing by the study sponsor
Interventional Template Version: 28 APR 2017

Protocol Summary

Title	Liposomal Bupivacaine (Exparel®) Plus 0.5% Bupivacaine HCL versus 0.5 % Bupivacaine HCL for Interscalene Nerve Block (ISB) for patients undergoing Total Shoulder Arthroplasty (TSA)
Short Title	Understanding the effects of Exparel® on post-operative pain management and opioid utilization for patients undergoing TSA
Brief Summary	This is a phase IV, randomized, single-blind, single-center study comparing patient related outcomes such as postoperative pain and opioid usage for patients who receive ISB's containing liposomal bupivacaine (Exparel®) plus 0.5% bupivacaine HCL versus 0.5% bupivacaine HCL undergoing total shoulder arthroplasty.
Phase	Clinical study phase IV
Objectives	To compare opioid utilization and pain management of patients who receive Exparel in an ISB vs standard 0.5% bupivacaine HCL during the initial 72-hour post-operative period. Additionally, to understand the duration of block after addition of Exparel® to bupivacaine in an Interscalene block after TSA
Methodology	phase IV, randomized, single-blind, single-center study
Endpoint	
Primary Endpoints: Opioid utilization expressed as (oral morphine mg equivalents) during the initial 72-hour post-operative period.
 
Secondary Endpoints: Duration of opioid use Patient reported pain scores (VAS) Length of stay Reported long-term narcotic use at home Documented opioid refills Adverse events such as respiratory depression, hypoventilation, reintubation, nausea, constipation

Study Duration	3 years
Participant Duration	Four weeks
Duration of IP administration	Once during surgery
Population	184 participants scheduled for total shoulder arthroplasty (TSA)
Study Sites	NYU Langone Orthopedic Hospital
Number of participants	184
Description of Study Agent/Procedure	Injection of 20mL 0.5% Bupivacaine HCL versus 10mL Liposomal Bupivacaine plus 10mL Bupivacaine 0.5% in an Interscalene block for TSA
Reference Therapy	Reference is Bupivacaine 0.5% for Interscalene block
Key Procedures	Interscalene nerve block with Liposomal Bupivacaine + Bupivacaine 0.5%
Statistical Analysis	Intention-to-treat analysis will be performed with mean, t-tests, within and between group ANOVA and linear regression,

CONFIDENTIAL

This material is the property of the NYU School of Medicine and Langone Medical Center. Do not disclose or use except as authorized in writing by the study sponsor

1 Key Roles

Principal Investigator:

[name]

Assistant Professor of Anesthesiology
Department of Anesthesiology, Perioperative care and Pain Medicine
NYU Langone Orthopedic Hospital
NYU Langone Health
[name]
[name]
[contact]

Co-Investigators:

[name]

Professor of Anesthesiology
Department of Anesthesiology, Perioperative care and Pain Medicine
NYU Langone Orthopedic Hospital
NYU Langone Health
[name]
[name]

[name]

Assistant Professor of Orthopedic Surgery
Department of Orthopedic Surgery
NYU Langone Orthopedic Hospital
NYU Langone Health
[name]
[name]

2 Background and Specific Aims

With the growing elderly population, the number of total shoulder arthroplasty (TSA) surgeries is increasing. Nationwide, the total and partial shoulder replacements increased from about 18,000 in 2000 to over 45,000 in 2013 according to the American Academy of Orthopedic surgeons (AAOS). One of the greatest drivers of cost following TSA has been shown to be discharge disposition. Effective pain control after surgery is paramount because it facilitates rehabilitation and decreases hospital length of stay. Additionally, it may increase the likelihood of patients being discharged to their home rather than a rehabilitation or skilled nursing facility.

TSA is a procedure that is well confined within the dermatomal distribution of an interscalene brachial plexus nerve block (ISB), making it an ideal procedure to both evaluate and compare the regional potential of varying agents. Although the analgesic coverage is typically ideal, single shot injection of the long acting

CONFIDENTIAL

This material is the property of the NYU School of Medicine and Langone Medical Center. Do not disclose or use except as authorized in writing by the study sponsor

local anesthetics, such as Bupivacaine, is limited in duration to the first postoperative day. Conversely, while interscalene perineural catheters offer the ability to continuously provide analgesia, they are time consuming to place, require daily maintenance, and often dislodge or migrate from the desired position. These limitations make interscalene perineural catheters problematic. In order to offer the longevity of an appropriately positioned catheter while preserving the simplicity of a single injection nerve blockade, this group proposes to evaluate the efficacy of liposomal bupivacaine or Exparel® in the setting of TSA.

Exparel® is a sterile, nonpyrogenic, preservative-free liposomal formulation of bupivacaine that provides a non-opioid option for postoperative pain control for up to 72 hours with single shot injection into the perineural space. The chemical and pharmacological nature of Exparel® allows for the encapsulated Bupivacaine to extend its duration of local anesthetic action by delaying medication release as compared to the injection of plain Bupivacaine. The FDA has recently approved Exparel® in its use for shoulder surgery via the interscalene nerve block. Exparel® has shown great potential with both its analgesic benefits and side effect profile; however, adequately powered trials are still necessary in order to compare its benefits to that of standard Bupivacaine.

To date, only one study has been published comparing bupivacaine alone to bupivacaine plus liposomal bupivacaine (1). In that study, the reduction in pain scores was minimal. However, there are several methodological issues with that study: 0.25% bupivacaine was used rather than 0.5%, resulting in a nerve block that was less dense, and making it mandatory to use general anesthesia; the study was probably underpowered; and analgesic use was not quantified.

2.1 Specific Aims

AIM 1: To determine if Liposomal bupivacaine added to 0.5 % bupivacaine HCL in the interscalene nerve block during TSA surgery significantly changes post-operative opioid usage during the initial 72 hours post-operative period. This will be evaluated by randomizing patients to either receive 0.5% Bupivacaine HCL or Bupivacaine 0.5% with Liposomal bupivacaine in the interscalene nerve block. Opioid consumption will be evaluated in the immediate post-operative period, up to 72 hours post op and for up to 4 weeks after surgery.

AIM 2: To determine if the addition of Liposomal bupivacaine to Bupivacaine 0.5% in an interscalene nerve block prolongs post-operative nerve block and hence reduces post-operative pain from during the initial 72 hour post-operative period. Using the same groups as above, the patient stated duration of block (record time of onset of pain) and post-operative VAS Pain scores will be recorded in both the hospital and outpatient settings. Physical therapy endpoints will also be monitored and recorded.

2.1 Statistical Hypotheses

We hypothesize that adding Liposomal bupivacaine to Bupivacaine 0.5% for the interscalene nerve block prior to TSA surgery will prolong the sensory block and reduce post-operative pain and opioid usage not only during the patients' inpatient hospital stay but also after discharge from the hospital for up to 72 hours. Furthermore, combining Liposomal bupivacaine and Bupivacaine will reduce complications associated with opioids such as constipation, nausea, pruritus, ileus and opioid dependency. Failing to reject the null hypothesis would signify that Exparel® has no clinically relevant impact on post-operative outcomes in TSA surgery as compared to plain Bupivacaine.

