5.1 Potential Risks

Bupivacaine used for this study is the standard of care for ISB. Liposomal Bupivacaine (EXPAREL®), a second study drug, has recently been approved by the FDA for use in interscalene blocks.

The potential risks associated with bupivacaine include neurologic and cardiac toxicity, if injected intravascularly. However, the risk is very low because a trained anesthesiologist using ultrasound guidance will perform the nerve block. This allows the anesthesiologist to see and avoid blood vessels when administering the medication. Additionally, the syringe of the local anesthetic will be aspirated prior to injection to ensure that the block needle tip is not intravascular.

The use of Liposomal Bupivacaine or Exparel® in this study is experimental and may cause side effects. Exparel® has recently been approved by the FDA to be used in interscalene blocks. The potential risks associated with Exparel® include nausea, constipation, and fever. In addition, there can be temporary sensory and motor loss, depending on the dosage, site of injection and duration of the nerve block. However, the amount (10mL) used in this study meets FDA dosage-regulations for this medication.

Potential Benefits

Study subjects may experience better pain control, improved satisfaction, decreased need for opioids and reduced incidence of side effects. If the study is not inconclusive, the study's results may benefit future patients by showcasing that Liposomal Bupivacaine improves pain control beyond 24hours in an ISB. Additionally, advocate for the use of Liposomal Bupivacaine as the standard of care for peri- and postoperative pain control in future patients undergoing TSA.

6 Statistical Analysis

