6.2 Analysis of Endpoints

Primary Endpoints:

Opioid utilization (expressed as oral morphine mg equivalents) used during initial 24-72 hours post-operative period after surgery.

Secondary Endpoints:

CONFIDENTIAL

This material is the property of the NYU School of Medicine and Langone Medical Center. Do not disclose or use except as authorized in writing by the study sponsor

Duration of opioid use
Patient reported pain scores (VAS)
Length of stay
Progress with physical therapy
Reported long-term narcotic use at home
Discharge location: home, acute rehab or skilled nursing facility
Documented opioid refills
Adverse events such as respiratory depression, hypoventilation, reintubation, nausea, constipation

The analysis of opioid use, VAS, and PROMIS assessments will rely on a univariate analysis of variance model for mean score. This model is in the class of models commonly known as unirep-ANOVA models. It assumes that the mean score is a function of elapsed time and the treatment regimen assigned. This model considers the fact that the subject's repeated measures are correlated. The fitted model will provide statistical estimates of the mean levels, the treatment-effect differences between mean levels, the standard deviation, the intra-class correlation coefficient, 95% CIs, standard errors (SE), and statistical hypothesis tests. The estimates of means will be used to compute summary criteria such as area under the curve (AUC) for each regimen. All estimates reported will be presented their 95% CIs.

All endpoints will be evaluated as fits the data set with graphical figures such as scatter plots, box-and-whisker plots, and frequency histograms to visualize the distribution of these outcomes and their relationships to covariates and treatment assignment. When appropriate descriptive graphical and tabular methods will also be estimated and presented in a graphical figure.

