6.3 Sample Size

184 subjects will be enrolled

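### Section 2.1 (Statistical Hypotheses) treats a failure to reject the null as proof of no clinically relevant impact, although no relevant difference is defined and non-rejection cannot show this.

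*Combined protocol and SAP*

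**What the plan says.** The protocol has two sections numbered 2.1; the point concerns the second, Statistical Hypotheses. It predicts that adding liposomal bupivacaine will prolong the sensory block and lower pain and opioid use. It adds that the combination "will reduce complications associated with opioids such as constipation, nausea, pruritus, ileus and opioid dependency". It then says how a null result is to be read: "Failing to reject the null hypothesis would signify that Exparel® has no clinically relevant impact on post-operative outcomes in TSA surgery", relative to plain bupivacaine.

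Other places bear on that sentence:

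- **Section 2 (Background)** reports that the one published comparison found a minimal reduction in pain scores. Among three methodological issues it lists that "the study was probably underpowered".
- **Section 4.6** expects about 184 enrolled to give 146 evaluable participants. The arm table in Section 3 plans 92 per arm.
- **Section 5.1**, under potential benefits, introduces a statement about future use of the results with "If the study is not inconclusive".
- **Section 6.2** plans a comparison of means over time and promises that "All estimates reported will be presented their 95% CIs". It plans no equivalence or non-inferiority test and sets no threshold for judging the intervals.
- **Section 6.3** consists of one line: "184 subjects will be enrolled".

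**The concern.** Failing to reject a superiority null means only that the data did not rule out zero difference. It does not mean that they ruled out a difference large enough to matter. That second claim needs a stated smallest relevant difference and an interval that excludes it. The protocol has the intervals but not the difference.

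Nor can the sentence be defended on the ground that the trial was sized to detect anything relevant, because no target difference, SD, alpha or power is given.

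The sentence also reaches widely. It speaks of one null hypothesis but concludes about post-operative outcomes in general. The same paragraph names opioid complications; if these are uncommon, non-rejection tells the reader least about them.

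If the sentence is followed, a non-significant result would be reported as no clinically relevant impact whatever effects its confidence interval still allows.

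**Working it through.** **1. Is a relevant difference defined?** Sections 2 to 6 contain none for opioid use, pain, block duration, length of stay or complications. The primary endpoint in Section 6.2, "Opioid utilization (expressed as oral morphine mg equivalents) used during initial 24-72 hours post-operative period after surgery", comes with no expected mean, difference or SD.

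**2. The plan's own figure.** The 146 cannot be derived, since its inputs are not given. Only the step to 184 can be checked. At an assumed 20% loss, 73/(1 − 0.20) = 91.25, rounded up to 92 per arm, so 2 × 92 = 184. The implied loss is 1 − 146/184 = 20.7%.

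**3. Inputs for an illustration.**

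- From the documents: 146 evaluable, or 73 per arm if losses are equal; 92 per arm with no loss.
- Assumed: two-sided alpha 0.05. The planned 95% CIs suggest it, and Aim 1 is worded without direction ("significantly changes post-operative opioid usage during the initial 72 hours post-operative period"), although the hypotheses are directional.
- Assumed: one value per patient, effects in SD units, and control complication rates of 10% to 50%.

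**4. Continuous outcomes (two-sample t).** The 95% CI half-width is t(0.975, 2n − 2) × √(2/n) in SD units.

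- 73 per arm: 1.977 × √(2/73) = 1.977 × 0.1655 = 0.327 SD.
- 92 per arm: 1.973 × √(2/92) = 1.973 × 0.1474 = 0.291 SD.

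Chance of failing to reject, from the noncentral t with noncentrality d/√(2/n):

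| True effect d | 73 per arm | 92 per arm |
|---|---|---|
| 0.3 SD | 56.3% | 47% |
| 0.4 SD | 33.0% | 23% |
| 0.5 SD | 14.9% | 8% |

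As one example, a non-significant estimate at z = 1.88 with 73 per arm is 1.88 × 0.1655 = 0.31 SD. Its interval is 0.31 ± 1.96 × 0.1655, or about −0.01 to 0.64 SD. It is compatible with no effect and with a moderate one.

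**5. Binary complications.** Chi-square without continuity correction, exact enumeration of both binomials, control rate p against p/2. The half-width with equal observed rates is 1.96 × √(2p(1 − p)/73).

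| Control rate p | Halving missed, 73 per arm | Halving missed, 92 per arm | Half-width, 73 per arm |
|---|---|---|---|
| 10% | 78.8% | 75% | 9.7 points |
| 20% | 60.1% | 52% | 13.0 points |
| 30% | 41.2% | 31% | 14.9 points |
| 40% | 23.8% | 15% | 15.9 points |
| 50% | 11.4% | 5% | 16.2 points |

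**6. Could this trial support the stronger claim?** Suppose the true difference is zero, there are 73 per arm, and the claim requires the whole 95% CI to lie within ±m. The chance of success, integrating over the estimated SD, is 34.0% for m = 0.4 SD and 70.2% for m = 0.5 SD.

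**The case against.** The strongest reply is that this is one loose sentence closing a hypothesis paragraph. Section 6, which governs the analysis, contains no such reporting rule. Section 6.2 requires estimates with 95% CIs, so a reader would see what a null result leaves open, and the remark under potential benefits shows that the authors accept the trial may be inconclusive. The background also calls for adequately powered trials, so the sentence may simply presume that this is one. On that view the real gap is the missing sample-size rationale in Section 6.3.

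Part of this stands. The intervals and the remark about an inconclusive study do soften the sentence, and the fault is one of wording. The background criticises an earlier study's power; it does not discuss how to read non-rejection, so the contrast with Section 2.1 is an inference, though a fair one. Calculating only at 73 per arm would be too narrow, so 92 is shown as well; the larger number lowers the miss rates but leaves the logic unchanged.

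The rest does not stand. Nothing in the protocol withdraws the sentence. The intervals have no threshold beside them, and the only stated way to read a null result is the one in Section 2.1. An unstated presumption of adequate power cannot support it. A sample-size rationale would help, but even a well-powered trial needs its interval compared with a stated difference before absence of a relevant effect can be claimed.

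**Conclusion.** The concern holds and should be fixed. The sentence draws a conclusion that non-rejection cannot support, and the protocol provides no relevant difference that could support it by another route. This rests on the text and not on the illustrative figures.

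Those figures assume two-sided 0.05, equal losses, one value per patient and roughly normal means. Opioid use may be skewed, and the repeated-measures model in Section 6.2 could give different widths. On those assumptions, effects of 0.3 to 0.5 SD would go undetected 15% to 56% of the time at 73 per arm (8% to 47% at 92). The consequence is confined to how a null result is interpreted.

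**What to change.** Delete the sentence in Section 2.1 (Statistical Hypotheses) and replace it with:

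> *A non-significant difference does not by itself show absence of a clinically relevant effect. Each outcome is interpreted from its estimated difference and 95% CI.*

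Section 6.2 already promises 95% CIs for every reported estimate, so nothing further is required. Because that section names a model only for opioid use, VAS and PROMIS, the team should make sure that the complication comparisons are also reported as differences with intervals.

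A margin is needed only if the sponsor wants to be able to claim no clinically relevant effect on the primary endpoint. In that case, the smallest relevant difference in oral morphine equivalents and the CI level should be fixed before any outcome data are seen by arm. The claim should be made only if the interval lies wholly within that difference.

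**Cost.** Wording only: no extra patients, data or tests. The sponsor gives up a strong statement after a null result, and the optional claim may be out of reach at this sample size, as step 6 of the working shows.

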2.2 Objectives and Purpose

The goal of this study is to determine the effectiveness of Liposomal bupivacaine at reducing opioid consumption from 24-72 hours when used along with Bupivacaine 0.5% for single shot ISB for total shoulder arthroplasty. In addition, we would also like to determine if Liposomal bupivacaine is effective at prolonging the sensory block and reducing post-operative pain in patients after TSA surgery. We would also

CONFIDENTIAL

This material is the property of the NYU School of Medicine and Langone Medical Center. Do not disclose or use except as authorized in writing by the study sponsor

like to determine how reduction in post-operative pain impacts a patient’s hospital stay in the short term. Primary outcomes measures will be opioid utilization (in morphine milligram equivalents [MME]) during a 72-hour post-operative period. Secondary outcomes include patient reported pain scores, VAS. While it is expected that the greatest benefit of Liposomal bupivacaine plus Bupivacaine 0.5% will be seen within 24-72 hours after surgery, it is possible that there will be in an overall reduction in long-term opioid use (up to 4 weeks). Secondly, function/rehabilitation, length of stay, and complications may be impacted by combined use of Liposomal bupivacaine plus Bupivacaine 0.5%.

3 Study Design and Endpoints

ARM 1: Experimental	Sample Size: 92	10 mL Bupivacaine 0.5% + 10 mL Liposomal Bupivacaine
ARM 2: Control	Sample Size: 92	20 mL Bupivacaine 0.5%

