4.6 Total Number of Participants and Sites

Recruitment will end when approximately 184 participants are enrolled. It is expected that approximately 184 participants will be enrolled in order to produce 146 evaluable participants. The only site for enrollment will be the NYU Langone Orthopedic Hospital.

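### Section 2.1 reads failure to reject the null as proof of no clinically relevant effect, which a superiority test without a stated margin cannot show

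*Combined protocol and SAP*

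**What the plan says.** The closing sentence of Section 2.1, Statistical Hypotheses, tells the reader how a null result will be understood: non-rejection of the "null hypothesis would signify that Exparel® has no clinically relevant impact on post-operative outcomes in TSA surgery as compared to plain Bupivacaine". It has no qualification and covers post-operative outcomes in general.

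The parts of the protocol that bear on this sentence are:

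- **Sample size.** Section 6.3 consists of one statement: "184 subjects will be enrolled". Section 4.6 adds that "approximately 184 participants will be enrolled in order to produce 146 evaluable participants". Neither section, nor any other, gives an alpha, a power, an SD, a target difference, a smallest relevant difference or an equivalence margin.
- **Precision.** Section 6.2 plans interval estimates: "All estimates reported will be presented their 95% CIs". It sets no value against which to read them.
- **An earlier trial.** Section 2 sets aside a published trial that found only a minimal reduction in pain scores, partly because "the study was probably underpowered".
- **An inconclusive outcome.** The Potential Benefits text in Section 5 makes the value of the results conditional: "If the study is not inconclusive".
- **The regimens.** The Protocol Summary gives the contrast as "Injection of 20mL 0.5% Bupivacaine HCL versus 10mL Liposomal Bupivacaine plus 10mL Bupivacaine 0.5% in an Interscalene block for TSA", and the arm table in Section 3 agrees with it.

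**The concern.** A superiority test that does not reject leaves two explanations open: the effect is too small to matter, or the trial was too imprecise to detect one that does matter. Only an interval estimate read against a stated relevant difference can separate them. Section 2.1 assumes the first explanation in every case and leaves no room for an inconclusive result.

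If that sentence guides the report, a non-significant estimate whose interval still contains a sizeable opioid reduction would be described as evidence that the drug does not help. Readers could then drop liposomal bupivacaine on inconclusive data. The sentence reaches every post-operative outcome, including the secondary ones, for which no power is stated either.

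**Working it through.** **1. The plan's own figure.** Section 4.6 goes from 146 evaluable to 184 enrolled. The implied loss is 1 − 146/184 = 20.7%. With an assumed 20% loss, 73/0.80 = 91.25 per arm, rounded up to 92, and 2 × 92 = 184. So 184 follows from 146. The 146 itself cannot be reproduced, because the inputs it would need are not given.

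**2. The logic, passage against passage.**

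| Place | Treatment of a small or null effect |
|---|---|
| Section 2 (earlier trial) | Not accepted as settling the matter, partly because power was doubtful |
| Section 5, Potential Benefits | This study might be inconclusive |
| Section 6.2 | Estimates with 95% CIs, no margin |
| Section 2.1 | Non-rejection equals no relevant effect |

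The last row cannot stand with the first two, and it makes no use of the third. This does not depend on any number.

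**3. How much a null could leave open (illustration).** Assumptions, none stated in the protocol: two-sample t-test, two-sided alpha 0.05 (matching the 95% CIs), equal arms, equal SD, no covariate adjustment. Evaluable per arm: 146/2 = 73.

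- Standard error of the difference = √(2/73) = 0.1655 SD.
- t(144; 0.975) = 1.977.
- 95% CI half-width = 1.977 × 0.1655 = 0.327 SD.
- An estimate that just misses significance therefore has a CI from 0 to 2 × 0.327 = 0.654 SD in favour of liposomal bupivacaine. This is the extreme case among non-significant results.

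Probability of non-rejection (1 − power) when a real difference exists:

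| True difference (SD) | 73 per arm | 92 per arm |
|---|---|---|
| 0.2 | 78% | 73% |
| 0.3 | 56% | 47% |
| 0.4 | 33% | 23% |
| 0.5 | 15% | 8% |

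With all 184 analysed (92 per arm), the half-width is 0.291 SD.

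**4. In MME.** The protocol gives no SD. For assumed SDs of 20, 40 and 60 MME, the half-width at 73 per arm is 0.327 × SD = 6.5, 13.1 and 19.6 MME.

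**5. What would support a conclusion of no relevant effect.** The CI must lie wholly inside ± a stated margin. With an observed difference of exactly zero and 73 per arm:

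- 95% CI: the margin must exceed 0.327 SD.
- 90% CI, which corresponds to two one-sided tests (TOST) at 5%: t(144; 0.95) = 1.656, and 1.656 × 0.1655 = 0.274 SD.

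By normal approximation, if the true difference is zero, the chance of meeting the 90% CI criterion with 73 per arm is 13%, 56% and 83% for margins of 0.3, 0.4 and 0.5 SD.

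**The case against.** The strongest reply is that this is a narrative sentence and not a decision rule. Sections 6.1 and 6.2 contain no instruction to declare absence of effect. Section 6.2 commits to treatment differences, standard errors and 95% CIs, and Section 5 accepts that the study could be inconclusive. No estimate, test or sample size depends on the sentence. That stands: the error affects the conclusion drawn and not the test, and a misreported null is a risk, not a certainty. It does not rescue the sentence, which was the only statement found of how a null result is to be read, and which appears under the heading for statistical hypotheses.

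A second reply is that the non-rejection figures describe any two-arm t-test of this size and would be the same if the sentence were deleted. That is also correct. They show what the inference would overlook; they are not a separate defect. They are only indicative, because Section 6.2 plans a repeated-measures model and opioid use is likely to be skewed.

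A reader might also infer two stronger points that the documents do not support:

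- **That the trial is underpowered.** With no target difference and no SD, this can be neither shown nor ruled out.
- **That the comparison is flawed because liposomal bupivacaine is described as added while half of the plain drug is replaced.** At 5 mg/mL, the plain dose is 10 × 5 = 50 mg against 20 × 5 = 100 mg. But the volumes are printed openly in the Protocol Summary, Section 3 and Section 3.1. The randomised comparison is valid, a favourable result is not undermined, and the 24–72 h primary outcome is little exposed. The documents show no early deficit in the experimental arm. What remains is that a null concerns the regimen tested, as in any trial.

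**Conclusion.** The concern holds as an error of inference in Section 2.1. Failure to reject would show only that no difference was demonstrated between the two regimens. It could not show that liposomal bupivacaine lacks a clinically relevant effect, because no relevant difference is defined and the sentence ignores the CIs that Section 6.2 already plans. It is also inconsistent with the protocol's own treatment of the earlier trial and of a possible inconclusive result.

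For scale, a true 0.4 SD benefit would go undetected about one time in three with 73 evaluable per arm (33%), and about one time in four with all 184 analysed (23%). The 95% CI half-width is about 0.33 SD and 0.29 SD respectively. These figures rest on the assumed alpha and the simple t-test. The logical point does not.

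**What to change.** Replace the closing sentence of Section 2.1, Statistical Hypotheses, with:

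*Failure to reject means that no difference was shown between 10 mL liposomal + 10 mL 0.5% bupivacaine and 20 mL 0.5% bupivacaine; the result will be interpreted from the 95% CI for the difference in 24–72 h MME.*

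The 24–72 h window follows Sections 6.1 and 6.2.

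If the sponsor wants to be able to conclude that there is no clinically relevant effect, two additions are needed:

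- State the smallest relevant MME difference before the interim safety and data analysis at 50 patients (Section 10.5). The board for that analysis consists of the principal investigator and co-investigators, and the section does not say whether data will be seen by arm. A deadline of final unblinding would therefore be too late to be safe.
- Require the CI for the difference to lie wholly inside that margin: the 90% CI for a conventional 5% TOST, or the 95% CI if a stricter standard is preferred. The margins in step 5 of the working show what 73 per arm can realistically support.

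The cost is a change of text and, if chosen, one agreed number. The CIs are already planned. Arms, doses, sample size and primary analysis do not change. The downside is a narrower claim after a null result.

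Describing the intervention as replacing half of the plain dose instead of adding to it (Protocol Summary, Specific Aims, Statistical Hypotheses) would be clearer, but it is optional and not part of the error.
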